The randomized repeated-measures design addresses threats to both internal and external validity and is strengthened by multiple replications (Shaddish, Cook, & Campbell, 2002). Caregivers will report treatments (i.e. medications) added during the 3 months to identify any potential influences. The Data Safety Monitoring panel will discuss new treatment developments and their impacts annually. Supervised training and monitoring protocols will assure fidelity. Measurement fidelity will be maintained by using measures with established reliability and validity and by research team training and monitoring. Research assistants (RAs) who code data will be blind to group assignment and video collection time to avoid expectation bias (Polit & Beck, 2007).

Aim 2. An exploratory descriptive design will identify PWD behaviors and precipitants captured in video that each caregiver identifies as their top priority. Content analysis and behavioral coding of videos will identify common behaviors (within the NDDCB framework), links to precipitants, and effective recommendations as a basis for a typology of caregiver interventions for in-home use (Dawson, et al., 1990). Actual caregiver use of interventions will be coded and audio recordings of team conferences will be transcribed and coded. Content analysis of this data will add information about characteristics predicting caregiver use of recommendations.

Aim 3. Caregiver satisfaction with effectiveness and ease of use will be evaluated and select caregivers will be interviewed and observed using FamTechCare. Video review team experts will rate the likelihood of diffusion into practice with a modified Duke Diffusion of Innovation in Long Term Care Battery (McConnell et al., 2010). Costs will be tabulated using traditional methods and compared to outcomes (PWD disruptive behavior and caregiver burden and NH placement intention), using traditional and Data-Envelopment Cost Analyses (DEA).

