D1. Sample. Eighty-eight dyads will be recruited from the University of Iowa Hospitals and Clinics (UIHC) and the University of Kansas Alzheimer's Disease Center (KU ADC). KU ADC is the area's major referral center with a clinic evaluating more than 300 new and 600 total patients annually. UIHC is the state and regional leader in tertiary care, providing research and clinical specialty care in Geriatric Psychiatry and Memory Disorders. It is estimated that 50% of family caregivers request professional assistance for managing disruptive behavior; so adequate study recruitment and enrollment is anticipated. If enrollment is not adequate, other dementia care providers (i.e. Alzheimer's Association) will be contacted.

Inclusion criteria for PWD are a diagnosis of AD or other dementia (moderate stage) and residing with a family caregiver who reports disruptive behavior management issues. Exclusion criteria include Huntington's disease, alcohol-related dementia, schizophrenia, manic-depressive disorder, deafness, and mental retardation. Participants with dementia of varied etiology will be included (a covariate factor). Electronic medical record search tools and dedicated research team time will facilitate identification of eligible participants. A trained research assistant (RA) will perform a Functional Assessment Staging of Dementia to confirm moderate dementia (Sclan & Reisberg, 1992) and the each caregiver will complete the Revised Memory and Problem Behavior Checklist (Roth et al., 2003) to verify the presence of disruptive behaviors on the initial home visit.

D2. Power. Sample size for this study was determined using power analysis for the primary hypothesis. The proposed sample size will provide sufficient power to detect between-group differences in outcomes (changes in proportions of behaviorally coded disruptive behaviors of PWD). In our previous research (Williams et al., 2009), the probability of PWD disruptive behaviors decreased from 55% to 26% when nurses used normal talk with PWD instead of elderspeak (patronizing communication similar to babble). We anticipate a similar 29% average decrease in the proportion of disruptive behaviors after the FamTechCare intervention. Applying this effect size as the difference between groups with a standard deviation of 35% in both and assigning a Type 1 error of 0.05 results in 93% power for detecting group differences after 3 months in 70 dyads (35 per group).

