FamTechCare Intervention. The telehealth nurse will review videos submitted by caregivers within 24 hours to facilitate emergency referrals (delirium, for example). FamTechCare caregivers will receive same-day nurse feedback (using standardized interventions) based on evidence-based protocols (see appendix C) developed by team experts and in the feasibility study (Niedens, 2010; Williams et al., 2012). Individualized, contextually-based interventions developed by the expert team (see examples in appendix D) will be provided to caregivers in their home at least weekly (after each video review meeting).

The telehealth nurse will review and select videos, leading the interdisciplinary team meetings for video review and intervention planning and will interact weekly with caregivers to provide feedback. The internet-based team meetings will be conducted using Zoom HIPPA-secure teleconferencing that supports live, interactive videoconferencing from different locations. Zoom teleconferencing is accessed using a unique weblink to a secure meeting. Using a share screen feature, all group members can watch the videos and simultaneously discuss and develop interventions.

Interventions will be documented on a behavioral care plan form modeled after other studies, providing individualized intervention instructions for a specific disruptive behavior (Burgio et al., 2009). Interventions will initially focus on nonpharmacological interventions. For example, pain interventions may first focus on assisting PWD to report pain, identify person-specific indicators of pain for caregivers to monitor, and teach pain control measures such as relaxation, distraction, and massage to the family caregiver. Our interdisciplinary team includes clinicians and investigators from KUMC and UIHC in partnership with a social worker from the Alzheimer's Association, and home-care nurses. Additional experts, such as a pain management nurse and speech and occupational therapists are available as needed to review videos.

Control Intervention. The control intervention is designed to be equivalent to FamTechCare for time and attention. Control group videos will be held for review and feedback after 3 months. Control caregivers will receive a weekly phone call from the nurse, who will provide standardized disruptive behavior management guidelines per protocol (see appendix C) (Niedens, 2010).

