The fixed effects in the model will include group (FamTechCare or control), site (UIHC or KU ADC), data collection time (baseline, 1, or 3 months), and all two-factor and three-factor interactions, including treatment by time interaction. A significant treatment by time interaction effect will indicate differences between the two groups. The analysis will be adjusted for important covariates, identified with baseline comparisons. With 70

subjects, 7 covariate factors meet statistical requirements for 5 to 10 subjects per covariate (Tabachnik & Fidell, 2001).

Fit of the models will be assessed using appropriate fit statistics, including Akaike information criterion (AIC) and likelihood ratio tests. To test for specific comparisons of interest, i.e. comparing treatment and control groups in terms of their mean change in PWD's disruptive behaviors, stress, and psychoactive medication use and caregivers' stress, burden, depression, sleep, and confidence (e.g., from baseline to month 3), tests of mean contrasts will be performed using parameter estimates from the fitted mixed models. Significant differences between the two groups, if they are in the expected direction, will support the hypothesis. An additional model per protocol will test changes in outcomes using only dyads in which the caregiver used recommended interventions in subsequent video recorded interactions.

D9b. Specific Aim 2. Identify precursors of disruptive behaviors and develop a typology of interventions for caregiver in-home use. We will use content analysis of caregiver submitted videos and recorded team video review meetings to tabulate the most common symptoms and behaviors. Qualitative content analysis of recorded team meetings for video review and written intervention plans for caregivers will identify key symptoms and behaviors. We will also code behaviors and symptoms exhibited by PWD in pre- and post-intervention videos submitted by caregivers. Counts will be analyzed descriptively to identify the most common symptoms and behaviors and the recommended interventions and their effectiveness.

D9c. Specific Aim 3. Evaluate ease of use, satisfaction, and cost effectiveness of FamTechCare using traditional cost methods and Data Envelopment Cost-efficiency Analysis (DEA).

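### Does D2 overstate power by applying a used-versus-not-used contrast to all randomized dyads with no allowance for non-use?

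*Combined protocol and SAP*

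**What the plan says.** D2 starts from the team's earlier work, in which the probability of disruptive behavior "decreased from 55% to 26% when nurses used normal talk with PWD instead of elderspeak". It then states: "We anticipate a similar 29% average decrease in the proportion of disruptive behaviors after the FamTechCare intervention". The calculation follows by "Applying this effect size as the difference between groups with a standard deviation of 35% in both", with a Type 1 error of 0.05, and reports 93% power at 3 months in 70 dyads. D3 enrolls 88 to allow for up to 20% attrition and makes no other allowance.

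In D9 (Specific Aim 1) the main analysis is a linear mixed model comparing the groups over baseline, 1 and 3 months: "A significant treatment by time interaction effect will indicate differences between the two groups". D9 adds a per-protocol model "using only dyads in which the caregiver used recommended interventions in subsequent video recorded interactions". The Aim 2 overview will look at "characteristics predicting caregiver use of recommendations".

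D4 has the nurse give control caregivers standardized guidelines from appendix C in a weekly call. Same-day feedback in the FamTechCare group rests on protocols from the same appendix. The Aim 1 overview and D7b both plan to code caregivers' use of interventions from the recordings, and D7b specifies coders blind to group and time.

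**The concern.** The 29 points come from a comparison by what was actually done: one style of talk against another. The powered test compares dyads as randomized, whether or not the caregiver acted on the advice. Carrying the figure across unchanged looks like assuming that every FamTechCare caregiver uses the recommendations and that no control caregiver does anything equivalent. The per-protocol model and the study of predictors of use show that the authors saw use as variable. The shared appendix C material means that the contrast might also shrink from the control side.

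D3 presents the final N of 70 as the number that the power analysis requires, and D2 concludes that the study is adequately powered. If the true all-dyads difference were well below 29 points, that conclusion would be too favorable for the primary hypothesis, and a null result might reflect low use and not an ineffective intervention.

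**Working it through.** **Inputs from the documents.** Difference 55 − 26 = 29 points, SD 35 points in both groups, Type 1 error 0.05 and 35 per group (D2); 44 per group enrolled with up to 20% attrition (D3). D2 does not state sidedness. Two-sided reproduces its figure; one-sided gives about 96%.

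**Reproducing the plan's figures.**
- Standard error of the difference: 35 × √(2/35) = 8.37 points.
- 29 / 8.37 = 3.47.
- Normal approximation: Φ(3.47 − 1.96) = 93.4%. Noncentral t with 68 degrees of freedom: 92.7%. Both agree with 93%.
- Attrition: 88 × 0.80 = 70.4, so 35 per group. This also agrees.

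**Sensitivity to non-use.** Let u be net use: the share using the recommendations in FamTechCare minus equivalent use in control. Suppose users change by 29 points and non-users by 0, and hold the SD at 35. The all-dyads difference is then 29 × u. The values of u are assumptions. Power is for a two-sided two-sample t-test:

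| Net use u | Difference (points) | Power, 35 per group | Power, 44 per group |
|---|---|---|---|
| 100% | 29.0 | 92.7% | 97.0% |
| 90% | 26.1 | 86.8% | 93.3% |
| 80% | 23.2 | 78.0% | 86.7% |
| 70% | 20.3 | 66.7% | 76.7% |
| 60% | 17.4 | 53.6% | 63.5% |

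**Break-even for 80% power.**
- With 35 per group, 23.78 points are needed: 23.78 / 29 = 82% net use (81% by the normal approximation).
- With 44 per group, 21.14 points are needed: 21.14 / 29 = 73%.

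**How far the result depends on the model (35 per group).**
- *Mixed users and non-users add variance.* Adding u(1 − u) × 29² to the FamTechCare variance, with no use in control, lowers power at 80% use from 78.0% to 75.9%. Break-even rises to 84%.
- *Non-users gain a quarter of the effect.* At 80% net use the difference is 29 × (0.80 + 0.20 × 0.25) = 24.65 points and power is 83%. At 70% it is 29 × 0.775 = 22.5 points and power is 75%.
- *Non-users gain half the effect.* At 70% net use the difference is 29 × 0.85 = 24.65 points and power is again 83%.
- *Users gain more than 29 points.* An all-dyads average of 29 needs 29 / 0.9 = 32.2, 29 / 0.8 = 36.25 or 29 / 0.7 = 41.4 points in users at 90%, 80% or 70% net use.

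The planned analysis is a covariate-adjusted mixed model over three time points, and its power is not computed here. The t-test stands in for it, as it evidently does in D2.

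**The case for a change.** The case for a change is that D2 never explains why an average over all dyads should equal a contrast between use and non-use. The word average alone does not answer this: at 80% net use it would require users to gain about 36 points, more than the earlier study showed. A per-protocol model would have little purpose if everyone were expected to use the recommendations. The least costly remedy would be a reworded sentence and one table from coding already planned.

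Part of this stands. The link from the earlier contrast to the trial's between-group difference is asserted without argument, and a sentence of justification would have been welcome.

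The rest does not carry. Providing for non-use is not a forecast of how much there will be. Nothing in the documents makes 29 points a ceiling for users: the earlier figure concerns one change in nurses' communication, whereas FamTechCare gives individualized expert feedback at least weekly for 3 months on three priority behaviors. Counting control use of general guidelines one for one against use of individualized recommendations is also unsupported.

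Nor would a null result be uninterpretable. Use is coded under Aim 1 and D7b, D7b relates it to dyad characteristics and to effectiveness, and blinding coders to group implies that recordings from both arms are coded. An analyst could tabulate use by arm without any amendment.

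**Conclusion.** No change is needed. D2's 93% is right for the difference it states, and D2 presents that difference as an average between the groups. The documents contain no use rate and name no 80% power target, so no stated figure is shown to be wrong.

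Power below 80% appears only under an added model (29 points in users, 0 in non-users, SD 35). Under that model it appears only when net use is below about 82% with 35 per group, or about 73% if all 44 per group contribute. D3 treats 20% attrition as an upper limit and the mixed model uses partly observed dyads, so the effective number probably lies between those two cases. Sizing at 93% leaves some room: power is still 87% at 90% net use with 35 per group.

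The possible remedies bring little. Enrolling more dyads would rest on an assumed rate. Recasting the power statement as about 24 points at 80% power would alter no analysis. A table of use by arm is a reporting choice that the planned coding already supports. What remains is an effect-size assumption justified more briefly than one would like.

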Recording. Behavior Capture (see appendix E) was developed by Behavior Imaging with NIH SBIR support for monitoring children with autism. **Behavior Capture** uses a "go-back-in time" buffering technology to record when triggered, also capturing video up to 15 to 30 minutes prior to the trigger (we will use a 10 minute "go back" as was effective in our feasibility study). Including antecedents enables effective behavior assessment. **Behavior Connect** provides automatic Internet transfer of video recordings to HIPAA-secure storage.

Feasibility of using this new technology for the FamTechCare intervention was established with 5 caregiver-PWD dyads in our CTSA feasibility study (Williams et al., 2012). We will use and adapt as needed the IRB-approved protocols and procedures, protocols for encrypted HMU units and software configuration using Site Kiosk (a program that limits computer use to research-specific programs), contracts to assure HIPAA protections of video data, and training materials developed by our CTSA study team. Computers will be configured to run the high definition, wide-angle webcam and remote control with preset settings, eliminating the need for caregivers to login with names and password (avoiding added burden). HMU computers run

continuously, ready for caregivers to record when they want feedback by simply pressing a button on the remote control (that fits in a pocket or is worn around the neck). A 5-foot webcam extension cord extends the recording area and the laptop itself is portable and easy for caregivers to move. Although no password is required for the caregivers to start recording, each HMU will connect to a separate account for discreet storage requiring a logon password to limit access and protect confidentiality of the data.

Both groups will record behaviors during daily care for 3 months using a HMU. FamTechCare group videos will be immediately uploaded via the Internet to a HIPAA-secure site for expert team review and feedback in behavior management. The time and attention equivalent control group will receive only a weekly phone call from a nurse, but recorded videos will be held for review and feedback at 3 months. This encourages participation (all participants will benefit from expert video review and feedback during their study involvement).

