D5. Procedures. Each site will identify potential participants and obtain consent. As soon as 4 participants are enrolled at each site, 2 will be randomly assigned to FamTechCare and the other 2 to the Control group. This is repeated until 11 cohorts are completed. A trained research assistant (RA) will make a home visit to collect demographic data and to complete FAST staging (Sclan & Reisberg, 1992) to confirm that the PWD has moderate stage dementia. Each caregiver will complete the Revised Memory and Problem Behavior Checklist (RMPBC) to verify the presence of disruptive behaviors. The RA will assist caregivers in identifying their 3 most problematic disruptive behaviors/care situations (see D7a) as the focus for recordings and interventions and the HMU will be set up in the area where the most disturbing disruptive behaviors usually occur (as the focus for the first week). The RA will train caregivers in HMU use and provide reference books. Visits will continue until caregivers demonstrate proficiency in recording and moving the HMU using a competency checklist. If the needed, the RA will make a home visit to assist the caregiver in moving the HMU in subsequent weeks.

Caregivers will be asked to record at least one video of their identified priority disruptive behavior/care activity each day. The telehealth nurse will monitor submitted videos and prompt caregivers with reminders if needed.

Caregivers will repeat recordings of each priority disruptive behavior/care activity after using FamTechCare interventions and at 1 and 3 months. Home visits to repeat data collection will be made at 1 and 3 months in both groups.

D6. Descriptive Data. Information about caregivers and PWD that may influence study outcomes will be collected and included as covariate factors (Unruh & Wan, 2004; Yu, Evans, & Sullivan-Marax, 2005; Zimmerman et al., 2005). PWD data will include gender and dementia etiology. Data on caregiver age, competency, relationship to the PWD, and research site will also be collected for covariate analysis.

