Behaviorally Coding of Disruptive Behaviors will be completed using our behavioral coding protocols from our NIH-funded R03 and R01 studies (Herman & Williams, 2009; Williams et al., 2009). We will use the Noldus Observer Video Pro (2003) software program to code disruptive behaviors, based on the operational definitions in the Resistiveness to Care scale (Mahoney et al., 1991). A computer key corresponding to each behavior state (disruptive or cooperative) is depressed when behaviors occur in the real time video recordings. Duration of each behavior state (disruptive or cooperative) is tabulated by the length of time keys remain depressed (until the key corresponding to the alternate, mutually exclusive behavior state is pressed). RAs will be trained using our protocol operational definitions for disruptive behaviors on practice materials until inter-coder agreement reaches 90% or greater. As in our prior studies, we will assess inter-coder agreement on 10% of actual study data. Retraining of coders will be provided if reliability falls below targets. RAs coding video will be blind to group and time of collection. Three recordings of videos of each priority care activity submitted at baseline, 1, and 3 months will be analyzed. The proportion of time disruptive behaviors occur will be compared within individuals and changes in the proportion of disruptive behavior compared between groups.

Caregiver-report Disruptive Behaviors. The 31-item Revised Memory and Problem Behavior Checklist (RMPB). (Roth et al., 2003; L. Teri et al., 1992) elicits caregiver reports of the behavior frequency related to 24 memory, depression, and disruptive behaviors in the past week, with Cronbach's alpha of .785.

PWD Stress. We hypothesize that FamTechCare interventions will reduce disruptive behaviors as well as stress in PWD.

PWD Medication Use. Counts of caregiver reported elective (prn) use of anxiolytics, hypnotics, and antipsychotic drugs taken by PWD in the past week will be compared between groups at 1 and 3 months.

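### The two-state video coding rule has no code for time when the person with dementia can be neither seen nor heard, so as written that time goes to the last active state

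*Combined protocol and SAP*

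**What the plan says.** **Coding rule (D7a, behavioral coding paragraph).** Coders press one key for disruptive and another for cooperative behavior while the recording plays. A state's duration accrues "until the key corresponding to the alternate, mutually exclusive behavior state is pressed". The outcome follows from these durations: "The proportion of time disruptive behaviors occur will be compared within individuals", with changes then compared between groups. The paragraph says that coding uses protocols from the team's earlier funded studies, and D7 describes these as adapted. They are not reproduced.

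**What is not written.** No section gives a code for time that cannot be observed, a rule for pausing the count, a definition of the denominator (whole recording or codable time), or a minimum observable time per recording.

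**Recording conditions (D4 and D5).** On the first visit "the HMU will be set up in the area where the most disturbing disruptive behaviors usually occur", as the focus for week one. Caregivers are trained to move the unit, and the research assistant can help in later weeks. D4 describes a wide-angle webcam and a portable unit, and adds: "A 5-foot webcam extension cord extends the recording area". Each recording includes 10 minutes from before the caregiver presses the button.

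**Role of the outcome (D2).** The sample size rests on "changes in proportions of behaviorally coded disruptive behaviors of PWD".

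**The concern.** With two mutually exclusive states and no way to end one except by starting the other, the rule leaves nowhere to put time when nothing can be observed. If the person leaves the room after the first key press, the last state keeps running. Someone who walks out upset goes on accruing disruptive time, and someone who wanders off calm goes on accruing cooperative time.

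Some unseen time is to be expected. The camera covers one area at a time, the caregiver places it after the first week, and the look-back footage was not staged for recording.

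The safeguards in D7a would not reveal the problem. Two blinded coders who apply the same rule to the same empty frame will agree with each other, so neither blinding nor the 90% agreement target detects it.

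The coded proportion sizes the trial. It also feeds the comparison of interventions under Aim 2 (D7b) and the cost-effectiveness ratio (D9c). Error in it therefore reaches several analyses, and the plan collects nothing that would show its size.

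**Working it through.** **Inputs from the documents (D2).** Difference 29 percentage points (55% to 26%), SD 35 points in each group, type I error 0.05 (taken as two-sided, since sidedness is not stated), 35 dyads per group, stated power 93%.

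**Assumed inputs.** The documents give no share of recording time that is unseen. Every unseen share below is an assumption, and so are the 20-minute clip and the 40% disruptive share.

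**1. The plan's own figure.** Standard error = 35 × √(2/35) = 8.37 points, and 29/8.37 = 3.47. Power is 93.4% by the normal approximation and 92.7% by the noncentral t (68 degrees of freedom). The stated 93% is reproduced.

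**2. Error in a single clip.** Take a 20-minute clip, with 55% of the observed time disruptive and the unseen time falling after the first key press.

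| Unseen | Observed disruptive time | Scored, last state cooperative | Scored, last state disruptive |
|---|---|---|---|
| 2 min | 0.55 × 18 = 9.9 min | 9.9/20 = 49.5% | 11.9/20 = 59.5% |
| 5 min | 0.55 × 15 = 8.25 min | 8.25/20 = 41.3% | 13.25/20 = 66.3% |

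The error can go either way. It applies to one clip and shrinks when several clips per visit and 35 dyads per group are averaged.

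**3. Constant unseen share f, scored cooperative.** Each proportion p becomes (1 − f)p, so the difference and the SD shrink by the same factor.
- f = 0.2: 23.2 points over SD 28.0, ratio 0.829
- f = 0.4: 17.4 points over SD 21.0, ratio 0.829
- Planned: 29 over 35, ratio 0.829

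Power stays at 92.7% in each case.

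**4. Unseen share that varies between dyads, unrelated to behavior.** With mean m and SD s of the share, the variance of the scored proportion is [(1 − m)² + s²](35² + μ²) − (1 − m)²μ², taking μ = 55 and 26 for the two groups.
- m = 20%, s = 15 points: SDs 29.7 and 28.8, root-mean-square 29.2. With a difference of 23.2, power is about 91%.
- m = 40%, s = 20 points: SDs 24.7 and 22.7, root-mean-square 23.7. With a difference of 17.4, power is about 86%.

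**5. Visibility that shifts by arm after baseline, no true effect.** The true share is 40% in both arms at both visits. Unseen time is 10% in both arms at baseline. At follow-up it is 10% in control and 30% in intervention, scored cooperative.
- Baseline: 0.9 × 40 = 36% in both arms
- Follow-up: 0.9 × 40 = 36% in control, 0.7 × 40 = 28% in intervention
- Change: 0 in control, −8 points in intervention; false difference in change −8 points

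With the arms swapped, the false difference is +8 points.

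**6. The same 10% and 30%, but stable from baseline.** Control is 36% at both visits and intervention is 28% at both visits. Both changes are zero, and so is the false difference in change.

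**The case against.** The strongest reply is that D7a summarizes coding protocols that the reader cannot see. They may contain an uncodable code or a pause rule. A reader might infer that unseen time will certainly be scored, but the documents show only that the written rule makes no provision for it. That part of the reply stands. It does not remove the point: the protocols are described as adapted, nothing says that they cover a home camera with look-back footage, and the one termination rule the plan reproduces has no third state.

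Three further inferences are tempting and are not supported.

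- **That every minute of a clip falls into one of the two states.** A key is pressed when a behavior occurs, so time before the first press belongs to neither. Someone who has not yet entered the room at the start of the look-back does not add cooperative time under the text as written.
- **That power drops well below 93%.** Shrinking the 29 points by 20% or 40% while holding the SD at 35 gives 78% or 54%. That requires all unseen time to be scored cooperative and the SD to stay put. A constant share scales both, and power does not move (step 3). If leaving view is unrelated to the current state, carrying that state forward mainly adds noise.
- **That any difference in visibility between arms creates a false effect.** The outcome is change from baseline. When there is no true effect, a stable difference cancels (step 6).

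It is also fair to say that the wide-angle lens, the cord, the movable unit and caregiver training reduce unseen time. They do not eliminate it.

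**Conclusion.** The point holds as a gap in a stated coding rule. As written, time after the first key press when the person is neither visible nor audible is added to the last active state, and the denominator of the proportion is not defined. This puts avoidable error into the outcome that sizes the trial.

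Bias in the treatment comparison needs more than unseen time. Time in view must shift differently by arm after baseline, or be linked to behavior, as when a person walks out while upset. The documents neither show nor exclude either. A shift by arm is conceivable because FamTechCare caregivers get feedback on their videos at least weekly while control videos are held for 3 months, which could change where and how caregivers record. The 8-point figure illustrates such a shift. It rests wholly on the assumed 40% disruptive share, the 10% and 30% unseen shares, and scoring as cooperative.

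The 93% power and the planned 70 evaluable dyads are not in error, and the fix changes neither. The change is worth making because it is cheap before coding starts, whereas adding the state later would mean recoding clips.

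**What to change.** 1. Add a third state, *not codable*, to the scheme in D7a, for time when the person is neither visible nor audible. Pressing its key ends the running state.
2. Define the outcome as disruptive time / (disruptive + cooperative time), and use this definition in D2, D7a and D9.
3. Fix a minimum codable time per clip before coding starts, and state what happens to clips below it.
4. Report codable minutes by arm and visit, so that a shift in visibility can be seen.
5. If the earlier coding protocols already contain such a rule, state it in D7a.

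The cost is one extra key, a short addition to coder training and a line in the analysis plan. A few clips below the minimum would be excluded.
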